2.4.6.6 Sample Size

55 patients

2.5 Management of Intercurrent Events

Should something interfere with the collection of data that is other than disconnection of the FHR devices or loss of power, these will be noted and the attempt to rectify the situation will also be documented. We will not however delay surgery in order fix the problem.

CONFIDENTIAL: This document is the intellectual property of [name]. Acceptance of this document constitutes the agreement by the recipient that no unpublished information contained herein will be published or disclosed without prior written approval.

Monitoring of maternal blood pressure and treatment of hypotension will follow standard routine protocol. Maternal blood pressure data and vasopressor therapy will be recorded in metavision as routine.

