2.4. Study Design

This will be an observational study to determine the feasibility of intraoperative FHR monitoring

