CONFIDENTIAL: This document is the intellectual property of [name]. Acceptance of this document constitutes the agreement by the recipient that no unpublished information contained herein will be published or disclosed without prior written approval.

Group 2 – Patients for scheduled cesarean section

- a) We will use the acoustic FHR sensor and the fetal ECG sensors.
- b) We will start with 5 patients and determine if we can capture fetal ECG. If this information correlates with the acoustic FHR, we then use only the fetal ECG sensors for the remaining 35 patients. We will adjust placement of leads for each group of 5 patient if there proves to be difficulty with capturing FHR intraoperatively, though all leads will be placed on the belly outside the sterile field or on the participant's back
- c) We will plan for an upper limit of 40 patients in this group

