2.4.6.3 Primary Outcome Measures

The primary endpoint of the feasibility study is the use of external abdominal wall fetal ECG sensors to assess FHR; its use-friendliness, the signal-noise ratio and the correlation with acoustic data.

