2.4.6.4 Secondary Outcome Measures

Secondary endpoints are the incidence of any non-reassuring FHR patterns during the "silent" period which is the period when the FHR monitor is removed, the patient's abdomen is scrubbed, sterile prep and drape until delivery of the fetus. If there are any non-reassuring FHR patterns (tachycardia, bradycardia, decelerations), maternal vital signs at the time will be noted.

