3.2 Sources of Materials

[figure not shown]
The source of data for the study will come from the patient's electronic record. This information includes fetal heart rate, patient blood pressure, dose of vasopressor, patient cardiac output, fetal blood gases.

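### Section 2.5 does not require FHR-device disconnection or power loss, or the attempts to fix them, to be documented, although both are technical failures in a technical feasibility study

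*Combined protocol and SAP*

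**What the plan says.** Section 2.5 (Management of Intercurrent Events) provides that should something "interfere with the collection of data that is other than disconnection of the FHR devices or loss of power, these will be noted". The same sentence adds that "the attempt to rectify the situation will also be documented". The next sentence says that surgery will not be held up to repair a problem.

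Section 2.4 describes the study as an "observational study to determine the feasibility of intraoperative FHR monitoring", and the synopsis gives technical feasibility as the objective. Section 2.4.6.3 defines the primary endpoint as the use of the fetal ECG sensors to assess FHR, naming "its use-friendliness, the signal-noise ratio and the correlation with acoustic data".

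Section 2.4.6 contains two rules that depend on capture:
- **Group 1** starts with 5 patients. If the fetal ECG captures FHR for the intended time (10 minutes is the aim), the study moves to the operating room. If not, another 5 induction patients are assessed, up to 15.
- **Group 2** (up to 40 patients) has this provision: "We will adjust placement of leads for each group of 5 patient if there proves to be difficulty with capturing FHR intraoperatively".

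**The concern.** In most trials a loose cable or a dead power supply is a nuisance outside the question being asked. Here it is part of the question. How often a monitor becomes disconnected or loses power in an operating room, and whether it can be restored while surgery proceeds, bears on technical feasibility and on use-friendliness. Section 2.5 sets up a duty to note interruptions and then leaves these two outside it.

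At stake is the completeness of the feasibility account. If the events occur and are not written down, a report built from the documented interruptions will leave out two direct kinds of technical failure, and the method may appear easier to use than it was. A lesser consequence is that, when the team decides whether Group 1 may progress or whether Group 2 leads should be moved, the written record need not say why a particular patient's FHR was not captured.

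**Working it through.** The point contests no figure. The plan's one relevant number, the sample size of 55, is reproduced by its group limits: 15 + 40 = 55. The documents give no interruption rate, no scale for use-friendliness and no capture threshold for Group 2, so no effect size can be calculated. The check is a reading of the sections against one another.

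1. **Scope of the duty (2.5).** The duty to note and the duty to document the remedy stand in one sentence and share one condition: that the cause is something other than device disconnection or power loss. The two named causes therefore fall outside both duties.

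2. **Does another section restore the duty?**
   - 2.4.6 (Observations and Measurements) describes the sensors and the stepwise rules but does not ask for the cause of lost capture.
   - 2.4.6.3 and 2.4.6.4 (outcome measures) list no count of interruptions.
   - 2.4.6.5 (Statistical Methods) does not mention interruptions or missing signal.
   - 3.2 (Sources of Materials) says of the data from the patient's electronic record: "This information includes fetal heart rate, patient blood pressure, dose of vasopressor, patient cardiac output, fetal blood gases". No device event is named. This is weak support, because the list may not be complete and the ECG comes from a separate system.
   - 3.2.2 (Data Management) describes the ECG capture system and the storage of paper and electronic data, but not the content of the paper data.

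   None of these restores the duty.

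3. **Could disconnection mean the planned removal of the monitor?** Section 2.4.6.4 refers to a period when the routine monitor is taken off for skin preparation. That meaning does not fit a sentence about interference with data collection, and it leaves power loss unexplained.

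4. **Does the gap touch what the study measures?** Technical feasibility is the aim (synopsis, 2.4), and use-friendliness is a named component of the primary endpoint (2.4.6.3). A monitor that becomes disconnected or loses power bears on both.

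5. **Does it touch a decision?** Progression in Group 1 and lead adjustment in Group 2 (2.4.6) both depend on whether FHR was captured. A disconnection or a power loss can produce a miss in either group, and the cause need not be on record when the decision is made.

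6. **What remains visible anyway?** The ECG is captured electronically (2.4.6, 3.2.2), so a gap may show. A gap does not by itself give its cause or the attempted remedy. Because surgery is not delayed (2.5), an unresolved interruption can leave a gap that is never filled.

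**The case against.** The strongest reply is that 2.5 says what will be noted for other interference and does not say that these two events will go unrecorded. The authors may have set them apart because they are foreseen and self-evident, and the team may know the cause without a note. This stands in part: the sentence permits recording. But the protocol gives no such reason, and what is merely permitted may be recorded unevenly.

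A second reply is that use-friendliness has no scale, count or threshold, so the documents cannot show that an unlogged disconnection would flatter it. This also stands in part, and it is why no size can be given. The undefined endpoint is the larger gap, but it does not make it sensible to leave two technical failures off the record.

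A reader might infer more than the documents support, in three ways:
- **That affected patients are dropped, which would inflate a capture rate.** With invented counts this looks large. Assume 40 cases, 4 failures from other causes and 8 from disconnection or power loss. Then 28/40 = 70.0% with all cases counted becomes 28/32 = 87.5% with the 8 removed. Both the counts and the removal are assumptions, and no section excludes any patient or minute.
- **That lead placement will be changed because of an unplugged cable.** This is possible, but the argument is thin. The failure most easily mistaken for poor placement is an electrode lifting off the skin, and that is not treated here as an exempt event. An unplugged or unpowered device would tend to show as absent signal rather than a noisy trace, though that is general reasoning and not from the documents.
- **That the number of groups of 5, or the share of patients monitored by ECG alone, measures the harm.** Such counts show where the record would be used, not how far any result would move.

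How much of the period before delivery was actually monitored, as a denominator for the secondary endpoint, is a separate question and is not part of this point.

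**Conclusion.** The point holds as a minor one. Followed as written, 2.5 lets a technical feasibility study omit the cause, frequency and attempted remedy of two direct technical failures. The feasibility and use-friendliness result may look better than it was. The amount cannot be computed from the documents and may be zero, either because no such event occurs or because staff note the events anyway. No stated figure changes.

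The conclusion rests on two things: the plain reading of the condition in 2.5, and the absence of any other section that requires these events to be recorded. It does not rest on any assumed event rate, nor on any exclusion of patients.

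**What to change.** In 2.5, delete the clause that sets aside device disconnection and power loss, so that every interruption is noted with its cause, approximate duration and attempted remedy. Count these interruptions in the feasibility and use-friendliness report. Have the causes available when the Group 1 progression decision and the Group 2 lead-adjustment decisions are made.

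The cost is one deleted clause and one more item to record per case. The note can be completed after the case, since an investigator may be scrubbed in. The documents describe no case form, so the team must decide where the item is kept. The feasibility result may look slightly less favourable. The rule that surgery is not delayed is untouched, and the sample size stays at 55.

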2.5.1 Adverse Experiences

The likelihood of adverse events is very low as the devices that will be used in the study are ones that have been used in the obstetric population for years. The participants, will however be monitored for adverse experiences. These events will be reported and the patients followed. The possible adverse events with this study are allergic reaction/skin sensitivity to the adhesive used for the fetal ECG, impression left on the subjects body from the Doppler.

2.5.2 Premature Discontinuation

Patients will be withdrawn from the study upon request. Patients will also be withdrawn from the study if it is believed to be in the best interest of the fetus or the patient. If a patient withdraws from any study in the series they will be replaced to maintain the estimated required number of patients for that particular study in the series.

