2.4.6 Observations and Measurements

This will be an observational study. We will first assess the fetal ECG monitors on a pilot group of patients for induction of labor who are not yet in active labor or in pain. We will then assess the technical feasibility of intraoperative FHR monitoring. Fetal heart rate will be assessed by:

a) External abdominal wall fetal ECG sensors placed at the top of the belly, outside the sterile field, or on the participant's back. This data is captured via BioSemi FLAT Active electrodes that interface with an ECG system that employs the algorithm ActiView to analyze the data. [See Appendix A].

[figure not shown]
b) An acoustic fetal heart sensor, as used routinely in labor will be used as a comparator in this feasibility study. When this device is used intraoperatively, sterility and acoustic contact are both maintained by placing the acoustic probe inside a sterile nylon sleeve containing electrode gel, and by using sterile electrode gel between the sterile sleeve and the abdominal wall. This technique may require the presence of an investigator "scrubbed into" the case to hold the abdominal wall probe (ie surgical scrub, sterile gown and gloves). This will be decided on a case-by-case basis. If needed, this investigator will need acoustic input to ensure adequate contact. So as not to distract the surgeon, this will be transmitted to the investigator by earphone input. These are scheduled cesarean deliveries and no fetal heart rate anomalies are expected; if there is an unexpected fetal bradycardia, this will be communicated to the surgeon.

c) Routine maternal vital signs (heart rate, blood pressure and oxygen saturation).

Group 1 – Patients for elective induction – not in active labor

- a) We will use the routine acoustic fetal heart rate sensor and try to determine the best placement of external abdominal wall fetal ECG sensors (either at the top of the belly outside the sterile field, or on the participant's back)
- b) We aim to capture 10 minutes of FHR with the ECG sensors comparing it to the acoustic monitor
- c) We will start with 5 patients. If we are able to capture FHR for the allotted period of time with the fetal ECG, then we will proceed to the intraoperative group. If not, we will assess another 5 elective induction patients.
- d) We will plan for an upper limit of 15 patients in this group

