2.5.4 Procedures to Minimize Potential Risks

Studies are conducted under the supervision of the PI and the co-investigators. The investigators are trained and experienced in performing research in human volunteer subjects. The investigators are anesthesiologists with extensive experience in the obstetric population. As this is an observational study, patients will be treated and monitored as per usual standards of care. All investigation will occur in an operating room on labor and delivery.

Inclusion and exclusion criteria, fasting requirements, monitoring, and the clinical protocol are designed to ensure that risks are absolutely minimal. Subjects are informed that participation is voluntary and they may refuse to participate and may withdraw from the study at any time without penalty.

CONFIDENTIAL: This document is the intellectual property of [name]. Acceptance of this document constitutes the agreement by the recipient that no unpublished information contained herein will be published or disclosed without prior written approval.

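### Does replacing patients who withdraw, with no stated analysis set, bias the feasibility results or the five-patient decisions?

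*Combined protocol and SAP*

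**What the plan says.** Section 2.5.2 provides for withdrawal on request and also on the team's judgement: "Patients will also be withdrawn from the study if it is believed to be in the best interest of the fetus or the patient". It then gives the replacement rule: "If a patient withdraws from any study in the series they will be replaced to maintain the estimated required number of patients". Section 2.5.4 tells subjects that "they may refuse to participate and may withdraw from the study at any time without penalty".

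Section 2.4.6 works in blocks of five. In Group 1 (elective induction, at most 15 patients) the target is a recording of stated length: "We aim to capture 10 minutes of FHR with the ECG sensors comparing it to the acoustic monitor". The block decision is: "If we are able to capture FHR for the allotted period of time with the fetal ECG, then we will proceed" to the intraoperative group; otherwise five more patients are studied. In Group 2 (scheduled cesarean) the first five have both sensors: "If this information correlates with the acoustic FHR, we then use only the fetal ECG sensors for the remaining 35 patients". The group ceiling reads: "We will plan for an upper limit of 40 patients in this group".

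Section 2.4.6.3 sets the primary endpoint as ease of use, signal-to-noise ratio and correlation with the acoustic data. Section 2.4.6.4 sets the secondary endpoint as the incidence of non-reassuring patterns. Section 2.4.6.5 names descriptive statistics and a ROC comparison, and section 2.4.6.6 gives 55 patients. None of these sections defines an analysis set or says how a withdrawn patient is counted. For interference with data collection, other than disconnection or power loss, section 2.5 says "these will be noted and the attempt to rectify the situation will also be documented".

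**The concern.** Replacing someone to keep a number up suggests that she is not part of that number. The rule has no time limit and withdrawal is open throughout, so it could reach a patient whose sensors were already on and whose monitoring was going badly. If she is replaced and not reported, the 40 in Group 2 become 40 completers, and her experience is lost from a study meant to show whether monitoring can be done at all. A best-interest withdrawal could also coincide with a non-reassuring pattern, which is the secondary endpoint.

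The blocks of five look most exposed. One patient is 1/5 = 20% of a block, and the blocks govern two decisions: whether to go into the operating room, and whether to drop the acoustic comparator for the next 35 patients.

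**Working it through.** **The plan's own figure.** 15 + 40 = 55; Group 1 is 3 × 5 = 15 and Group 2 is 5 + 35 = 40. The sums agree. No precision target, withdrawal rate or capture criterion is given, so every other input below is an assumption. A capture proportion is not itself a stated endpoint; it serves here only as a yardstick.

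**Step 1: is it replacement or exclusion that matters?** Assume 35 of 40 captured and one failed patient withdrawing. An average replacement adds 0.875 of a success.

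| | No replacement | Replaced |
|---|---|---|
| Withdrawn patient kept | 35/40 = 87.5% | (35 + 0.875)/41 = 87.5% |
| Withdrawn patient left out | 35/39 = 89.7% | (35 + 0.875)/40 = 89.7% |

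The rows differ and the columns do not. Replacement is neutral; only exclusion moves the figure, and section 2.5.2 does not call for exclusion.

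**Step 2: how large could exclusion be in Group 2?** Let k withdrawn patients be left out.

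- Capture, assuming 36/40 = 90.0% is reported (exact 95% CI 76.3% to 97.2%, a width of 20.9 points). The full figure lies between 36/(40 + k) and (36 + k)/(40 + k). For k = 1: 36/41 = 87.8% to 37/41 = 90.2%. For k = 2: 36/42 = 85.7% to 38/42 = 90.5%.
- Non-reassuring patterns, assuming 2/40 = 5.0% is reported. For k = 1: 2/41 = 4.9% to 3/41 = 7.3%. For k = 2: 2/42 = 4.8% to 4/42 = 9.5%.

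The largest shift from one patient is 90.0 − 87.8 = 2.2 points for capture and 7.3 − 5.0 = 2.3 points for patterns.

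**Step 3: the blocks of five.** Assume that a pass needs all five captured (the plan states no such rule), that true capture is p, that a share q of failed patients withdraw and are replaced uncounted, and that captured patients never withdraw. The pass chance is [p/(1 − (1 − p)q)]^5.

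| p | q = 0 | q = 0.10 | q = 0.25 |
|---|---|---|---|
| 0.7 | 16.8% | 19.6% | 24.8% |
| 0.8 | 32.8% | 36.3% | 42.3% |
| 0.9 | 59.0% | 62.1% | 67.0% |

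For p = 0.8 and q = 0.25: (0.8/0.95)^5 = 42.3%. If captured and failed patients are equally likely to withdraw, the chance returns to p^5, or 32.8% at p = 0.8.

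**Step 4: does the plan route failures into withdrawal?** Failed capture is not a ground for withdrawal. In Group 1 it leads to another five patients, and in Group 2 to moving the leads. Interference is noted and surgery is not delayed. An unexpected bradycardia is communicated to the surgeon, and non-reassuring patterns are counted as an endpoint. A patient with a poor signal who stays in the study is never replaced. Only a request to leave, or a best-interest withdrawal, made after the sensors are on could produce the effect in steps 2 and 3.

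**The case for a change.** The strongest case for a change is that in a feasibility study a patient who does not complete monitoring is part of the result, yet the plan would let a report of 40 completers pass without mention of the others. It does not say whether 15 and 40 count enrolled or completed patients, or whether a withdrawn patient counts in her block. Dropping the acoustic comparator cannot be undone for patients already recorded without it. The natural remedy, replacing only before sensor application is attempted and analysing everyone after that, needs only new wording.

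The silence is real, and so is the possibility of a best-interest withdrawal during a non-reassuring pattern. The rest is weaker. It is an inference, not the text, that a withdrawn patient falls outside the 40 or outside her block; section 2.5.2 does not mention blocks. Limiting replacement would remove no bias, as step 1 shows, and it has a cost. If the comparator is dropped after the first five Group 2 patients, one unreplaced withdrawal among them could leave four complete paired intraoperative recordings for the correlation in the primary endpoint. The present rule protects that number.

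**Conclusion.** No change follows. The replacement rule is sound: it keeps up the number of complete recordings and introduces no bias of its own. The gap is that nobody wrote down who is analysed. For a descriptive feasibility study the sensible reading is to use what was recorded up to withdrawal, subject to consent, count the patient in her block, and report withdrawals with timing and reason. The plan permits all of this as it stands.

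The size of any bias is unknown, because the documents give no withdrawal rate. It is probably small, since monitoring is short and external. On the assumed inputs, leaving out one patient shifts a Group 2 proportion by at most about 2 points, against an interval of about 21 points. The larger block effects, such as 32.8% rising to 42.3%, rest on an all-five pass rule that the plan does not state and on a quarter of failed patients, but no captured ones, withdrawing. If withdrawal is unrelated to monitoring or fetal condition, the bias is zero. The judgement would change only if several patients withdrew after sensor application for reasons tied to the monitoring and were then left out of the report.

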2.5.3 Potential Risks

[figure not shown]
The potential risks in this study series involve the potential side effects/reactions to the electrocardiogram adhesive, Doppler and the psychological effects of being involved in a study. We do not anticipate risks related to privacy invasion or socio-economic status.

2.5.4 Procedures to Minimize Potential Risks

Studies are conducted under the supervision of the PI and the co-investigators. The investigators are trained and experienced in performing research in human volunteer subjects. The investigators are anesthesiologists with extensive experience in the obstetric population. As this is an observational study, patients will be treated and monitored as per usual standards of care. All investigation will occur in an operating room on labor and delivery.

Inclusion and exclusion criteria, fasting requirements, monitoring, and the clinical protocol are designed to ensure that risks are absolutely minimal. Subjects are informed that participation is voluntary and they may refuse to participate and may withdraw from the study at any time without penalty.

CONFIDENTIAL: This document is the intellectual property of [name]. Acceptance of this document constitutes the agreement by the recipient that no unpublished information contained herein will be published or disclosed without prior written approval.

